5. OBJECTIVES & ENDPOINTS

5.1. Primary objective

The primary objective of this study is to demonstrate that the cure rate after local application of test product is better than a predefined limit. The test product must achieve a cure rate superior to 70% (at the end of day 10, corrected for re-infestation).

To compare efficacy and safety of test product against reference product in subjects, infested with head lice (*Pediculus humanus capitis*).

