5.2. Secondary objectives

Secondary objectives refer to comparison of the cure rate of test product with those of reference product using the following endpoints:

Secondary efficacy objectives:

- a) To show that the cure rate at the end of day 10 (corrected for re-infestation) for the reference product for all baseline infestations is better than 70%.
- b) To show that the test product has a cure rate superior to that of the reference product.
- c) In case that superiority cannot be shown: to show that the test product is non-inferior to reference product regarding cure rate. A non-inferiority margin of 7.5% will be used.

Further secondary objectives refer to objectives c and d, however evaluated in subgroups or other time points.

- d) Efficacy of the investigational products for head lice for mild and moderate baseline infestations (cure rate at the end of the study day 10, corrected for re-infestation).
- e) Efficacy of the investigational products for head lice for all baseline infestations (cure rate at day 1).
- f) Efficacy of the investigational products for head lice for mild and moderate baseline infestations (cure rate at day 1).

As further secondary objectives, safety and tolerability of test product or reference as well as the acceptance of the investigational products will be evaluated.

Secondary safety objectives;

- g) To evaluate local tolerability by subject: subjective symptoms (burning, paraesthesia, pruritus): 0h, 1h, 24h, 7d and 10d p.a. (descriptive evaluation).
- h) To evaluate global tolerability by the subject and study staff (number of subjects with global tolerability ratings of “very good”, “good”, “moderate”, “poor”, descriptive evaluation) at 10d

after application.

- i) To evaluate skin irritation by study staff (secondary infection, erythema, excoriation) on day 0, 1, 7 and 10.
- j) To evaluate eye irritation by study staff on day 0, 1, 7 and 10.
- k) To evaluate characterization of safety and tolerability of the investigational products considering Adverse Events in the study population.

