6. INVESTIGATIONAL PLAN

6.1. Study Design

This dual-centre, randomized, controlled, investigator-blinded, comparative study will be conducted in 70 subjects (male and female subjects; age ≥ 2) with confirmed diagnosis of head lice infestation. All subjects will be randomized in a 1:1 ratio in both treatment groups.

In this study, a repeated treatment will be performed, as described in the literature. For two-treatment protocols, it is recommended that the second treatment should be applied on day 7 to day 8 and the final assessment should be on day 10 [15]. In total, 4 visits are planned:

- Visit 1 – Baseline visit (Day 0; first treatment)
- Visit 2 – Post treatment evaluation visit (Day 1: 24hrs +/- 3 hrs.)
- Visit 3 – 2nd treatment visit/evaluation (Day 7 + 1 day)
- Visit 4 – Final evaluation visit (Day 10 + 2 days)

Subjects complying with the in- and exclusion criteria will receive the study medication according to a subject number, allocated in ascending order in correspondence with their inclusion into the study. Both investigational products will be tested as described in the product leaflets in compliance with the above-mentioned treatment recommendations.

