8. STUDY POPULATION

8.1. Number of Subjects

In total, 70 subjects ages 2+ years and older will be enrolled in the study. Based on previous clinical data with comparable head lice products, a power analysis has been performed. Results indicated that a sample size of 35 subjects in each treatment group results in a power of 80%, considering a cure rate of 95% for

the test product and 55% for the reference product and a superiority margin of 15%. In case of dropouts, subjects will not be replaced.

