10.2. Data Analysis Considerations

Based on previous clinical data with comparable head lice products, a power analysis has been performed. In order to detect superiority (superiority margin of 15%) of the test product (cure rate of 95%) over the reference product (cure rate 55%) with a power of 80% at 5% level of significance, 30 subjects are needed per treatment group.

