10.4. Efficacy Analyses

Efficacy analyses will be performed on the ITT population, consisting of all subjects who were included and randomized in the study, with available baseline value of the primary endpoint and at least one follow-up visit for the efficacy parameters. All statistical test will be performed at a 5% level of significance.

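### Every test is run at 5% and two different tests carry primary status, with no hierarchy or exploratory label for the reference-limit, mild/moderate and Day 1 evaluations

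*Combined protocol and SAP*

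**What the plan says.** - **Level.** Section 10.4: "All statistical test will be performed at a 5% level of significance". Whether tests are one- or two-sided is not stated.
- **Primary.** Section 5.1 first requires the test product's Day 10 cure rate to exceed 70%. It then adds, under the same heading, "To compare efficacy and safety of test product against reference product in subjects". Section 10.4.1 repeats the 70% aim but writes H0,prim as a zero difference between arms, with an alternative of more than 15 points, tested by a chi-square test of independence. Section 5.3 names one primary endpoint, the test product's own Day 10 cure rate, and calls the difference between arms secondary, as does 5.2b.
- **Secondary.** Section 5.2a sets a 70% test for the reference product. Objectives d, e and f cover mild/moderate infestations at Day 10, all subjects at Day 1, and mild/moderate infestations at Day 1. They are introduced by "Further secondary objectives refer to objectives c and d, however evaluated in subgroups or other time points".
- **Order.** Section 10.4.1 tests non-inferiority (margin 7.5%) if superiority is not shown. Its remark that multiplicity needs no correction belongs to that switch alone.
- **Sizing.** Section 10.2 bases the sample size on the comparison: "with a power of 80% at 5% level of significance, 30 subjects are needed per treatment group".

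**The concern.** A reader cannot tell which test decides the trial. If the product exceeds 70% but does not beat the reference, 5.3 supports calling the trial positive. If it beats the reference but does not clear 70%, H0,prim in 10.4.1 supports the same claim. Behind these stand the reference-limit test and three evaluations in a subgroup or at another time, each at a nominal 5% and none labelled exploratory.

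The cross-reference in 5.2 adds to the uncertainty. Objectives d-f are tied to c and d, so d refers to itself, c is non-inferiority, and superiority (b) is not named. What is to be tested in d-f is therefore undefined. With about 35 subjects per arm, a missed Day 10 comparison would leave room to emphasise a Day 1 or subgroup result after the data are seen.

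**Working it through.** **1. The plan's own figure, to find the sidedness.** Section 10.2 assumes a "superiority margin of 15%) of the test product (cure rate of 95%) over the reference product (cure rate 55" per cent), 80% power and 5% significance. With n = (z_α + z_β)² × [p₁q₁ + p₂q₂] / (p₁ − p₂ − margin)²:
- One-sided 5%: (1.645 + 0.842)² × (0.0475 + 0.2475) / 0.25² = 29.2, so 30. This matches 10.1 and 10.2.
- Two-sided 5%: (1.960 + 0.842)² × 0.295 / 0.0625 = 37.05, so 38. No match.

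The sizing therefore points to one-sided 5% with the margin inside the test. The chi-square test in 10.4.1 tests zero difference without a margin. Both readings are carried below. Section 8.1 plans 35 per group, and 6.1 allocates 1:1.

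**2. Count of tests.** Six: (i) test product against 70%; (ii) test against reference at Day 10; (iii) reference against 70%; (iv)-(vi) the comparison as in d, e and f. Tests (iv)-(vi) are a reading of 5.2, since section 10 writes no hypothesis for them. If all were independent, the bound would be 1 − 0.95² = 9.75% for two tests and 1 − 0.95⁶ = 26.5% for six. They are correlated, so the true figures are lower.

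**3. The 70% test alone.** An exact binomial test with 35 subjects needs 30 cures: P(X ≥ 30 | 0.70) = 2.7%, while 29 would give 6.5%. Its own error is below 5%.

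**4. Correlated tests, by simulation.** The documents give no subgroup share, Day 1 cure rate or Day 1/Day 10 correlation, so these are assumed. The null is equal arms, both at 70% on Day 10, with no difference at Day 1.

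| Tests counted | Setting | At least one significant |
|---|---|---|
| Two called primary | binomial counts, 30 or 35 per arm | 6.0-6.5% |
| Two called primary | large-sample, one-sided, or two-sided in either direction | 8.0-8.3% |
| Two called primary | favourable only, difference test at 2.5% per side | 4.2-4.5% |
| All six | binomial counts, share 0.6-0.85, correlation 0.4-0.8 | 14.3-18.5% |
| All six | large-sample, share 0.5-0.9, correlation 0.2-0.8, one-sided, or two-sided in either direction | 15.5-21.8% |
| All six | large-sample, two-sided, favourable only | 8.9-11.8% |
| Four comparisons | 35 per arm, two-sided, either direction | 13-15% |
| Four comparisons | same, favourable only | about 7% |
| Four comparisons | same, one-sided 5% | 12-15% |
| Four comparisons | same, 15-point margin applied in the test | 0.2-1.2% |

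The four-comparison rows assume Day 1 cure of 50-70%, a mild/moderate share of 70-80% and a latent correlation of 0-0.6.

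**5. Dependence on the null.** At the planned reference rate of 55%, test (iii) would succeed with probability P(X ≥ 30 | 35, 0.55) = 0.01%. It adds error only if the reference truly lies near 70%.

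**The case against.** The strongest reply is that 5.3 names a single primary endpoint. If that alone is confirmatory, its error is at most 5% (2.7% by exact test), and the plan nowhere promises 5% across all objectives. This stands as far as it goes. A reader might infer that an error rate of 13-17% replaces a promised 5%, but the documents do not support that. No family-wise rate is stated, the figure needs assumed inputs, and it counts results against the test product as well as for it. The reply does not settle the matter, because 5.1 and 10.4.1 also give the comparison primary status.

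Second, d-f have no written hypothesis, and c is non-inferiority, so three further superiority tests are an inference. That is fair. The inference is still the natural one: 5.2 introduces the secondary objectives as comparisons between products, and it marks g and h as descriptive but not d-f.

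Third, if superiority must exceed the 15-point margin, false claims among the four comparisons are about 1% or less. This also stands, but the test named in 10.4.1 does not apply the margin.

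A reader might further infer that the subgroups leave out the class in which failure is likeliest. Section 6.2 only defines severity by louse counts and says nothing about cure by class. Severe infestations also remain in the primary endpoint. That inference should not be drawn.

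**Conclusion.** The concern holds as a gap in the plan. Two tests compete for primary status, every test is at 5%, and nothing beyond the superiority/non-inferiority switch orders the others or labels them exploratory. The cross-reference for d-f is also faulty.

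The size is conditional on equal arms at 70%, 30 or 35 per arm or a large-sample approximation, zero-difference tests, and assumed subgroup share, Day 1 rate and correlation. On that basis it is about 4-8% for the two tests called primary and about 14-22% for all six (one-sided 5%, or two-sided counting either direction). For a favourable result among the four comparisons it is about 7% two-sided or 12-15% one-sided. With the margin in the test it is about 1% or less. These figures show how much depends on choices that the plan leaves open; they are not a breach of a stated error rate. The change should be made before the data are seen.

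**What to change.** State one fixed sequence in 10.4, each step at 5% and only if the previous step succeeded:
1. Test product above 70% at Day 10. Write it in 10.4.1 as H0,prim with its own one-sample test (for example exact binomial), matching 5.3 and the first paragraph of 5.1.
2. Test against reference at Day 10 in all subjects, with non-inferiority (7.5%) and superiority both inside this step. Say which result opens step 3. A Day 1 superiority claim should require Day 10 superiority first.
3. The same comparison at Day 1 in all subjects.

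If the sponsor means the comparison, on which the trial was sized, to be primary, swap steps 1 and 2 and align 5.1, 5.3 and 10.4.1. That is the sponsor's design decision. In either case state the sidedness and whether the 15-point margin is part of the test.

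Reword 5.2a, d and f as descriptive estimates with 95% intervals, and add the severe class. With the 70% limit as primary, move the second paragraph of 5.1 to 5.2 or remove it. Correct the cross-reference in 5.2 so that only e refers to b and c.

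The cost is protocol and SAP wording; sample size and data collection do not change, and the first test keeps its full 5%. The sequence holds the error across its confirmatory tests at 5% or less. The downside is that a Day 1 result cannot be claimed if an earlier step fails, and subgroup results remain descriptive.

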10.4.1. Analysis of primary objective

The cure rate (p) corresponds to the proportion of subjects who are cured at day 10 among all subjects that received any treatment at day 0. The aim of the study is to show superiority for the cure rate of the test product versus a predefined limit of 70%.

The following null hypothesis will be tested:

$$H_{0, \text{prim}}: p_T - p_R = 0 \text{ and } H_a: p_T - p_R > 15\%$$

A χ^2 -test of independence will be used to test the null hypothesis.

In case superiority could not be proven, non-inferiority will be tested. According to ICH guideline “Points to consider on switching between superiority and non-inferiority” [17], it is allowed to assess non-inferiority in to the absence of superiority. Prerequisites include:

- predefinition of a non-inferiority margin
- no correction in terms of multiplicity

As non-inferiority margin (δ), a 7.5% worse cure rate is regarded as clinically not relevant. The following null hypothesis will be used: $H_{0, \text{NI}}: p_T - p_R < \delta$, whereby $\delta = -7.5\%$. The lower, 95% confidence interval (CI) of the difference $p_T - p_R$ will be used for the test. If $H_{0, \text{NI}}$ will be rejected, non-inferiority cannot be shown.

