5.3. Endpoints

The primary endpoint is the cure rate at the end of day 10 (corrected for re-infestation) for the test product for all baseline infestations.

The secondary endpoint is the difference of cure rates (as defined as primary endpoints) between both treatments.

Safety endpoints are the secondary characteristics of the lice infestation (see Section 9.4) and reported adverse events.

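### The stated primary objective (test-product cure rate above 70%) has no test: the plan assigns it a two-arm chi-square, which cannot support the 15-point margin either

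*Combined protocol and SAP*

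**What the plan says.** Section 5.1 sets a fixed limit: "The test product must achieve a cure rate superior to 70" percent, at day 10 and corrected for re-infestation. A second sentence under the same heading adds a general comparison: "To compare efficacy and safety of test product against reference product in subjects, infested with head lice".

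Section 5.3 is consistent with the fixed limit: "The primary endpoint is the cure rate at the end of day 10 (corrected for re-infestation) for the test product". It places the comparison between arms one level down: "The secondary endpoint is the difference of cure rates (as defined as primary endpoints) between both treatments". Section 5.2 b likewise lists superiority over the reference as a secondary objective, without a margin.

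Section 10.4.1, on the analysis of the primary objective, restates the fixed limit: "The aim of the study is to show superiority for the cure rate of the test product versus a predefined limit of 70" percent. The hypotheses that follow, labelled primary, are H0: pT − pR = 0 and Ha: pT − pR > 15%, and a chi-square "test of independence will be used to test the null hypothesis". Non-inferiority at −7.5% follows if superiority is not shown.

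The sample size in section 10.2 is also two-armed: "In order to detect superiority (superiority margin of 15%) of the test product (cure rate of 95%) over the reference product", with the reference at 55%, 80% power and a 5% level.

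**The concern.** There are four faults in one place.

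1. No test or confidence interval sets pT against 70%. The only interval named is for pT − pR, and it serves the non-inferiority step.
2. The between-arm difference is a secondary endpoint in section 5.3 but is analysed as primary in section 10.4.1.
3. The null and the alternative are not complementary. True differences between 0 and 15 points belong to neither.
4. A chi-square of independence tests pT = pR only. Rejecting it is not evidence that the difference exceeds 15 points.

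A statistician who follows the text exactly could declare the primary objective met without examining it, or missed when the cure rate is plainly above 70%. Choosing the correct test after the data are in would forfeit prespecification of the primary claim.

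**Working it through.** **Inputs from the documents.** pT = 95%, pR = 55%, superiority margin 15 points, power 80% (sections 8.1 and 10.2); 35 per arm (section 8.1) or 30 per arm (sections 10.1 and 10.2); 5% level with sidedness not stated (section 10.4); limit 70% (sections 5.1 and 10.4.1).

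**Assumptions.** Two-sided 5% for the chi-square, counting only results that favour the test product. Continuity correction is not specified, so both versions are shown. Rates marked * are not in the documents.

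**Step 1. Which test was powered?** For superiority by a margin with unpooled variance:

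n = [pT(1−pT) + pR(1−pR)] (zα + zβ)² / (pT − pR − 0.15)²

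- One-sided 5%: (0.0475 + 0.2475)(1.645 + 0.842)² / 0.25² = 29.2, so 30 per arm. This reproduces section 10.2.
- Two-sided 5%: 0.295 × (1.960 + 0.842)² / 0.0625 = 37.05, so 38 per arm.
- Ordinary chi-square with null difference 0: 18 per arm two-sided, 14 one-sided (22 and 19 with continuity correction).

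The stated 30 comes from a null difference of 15 points. The planned chi-square has a null difference of 0, so it is not the test that was powered.

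**Step 2. What the chi-square does at 35 per arm.** With x and y cured in the two arms, sum Bin(x; 35, pT) × Bin(y; 35, pR) over all pairs with x > y and

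(x − y)/35 ÷ √[2 p̄(1 − p̄)/35] > 1.96, where p̄ = (x + y)/70.

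The corrected version subtracts 1/35 from the difference.

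| pT | pR | Truth | Significant, uncorrected | Corrected |
|---|---|---|---|---|
| 70% | 55% | 70% not exceeded; difference exactly 15 | 25.4% | 18.7% |
| 70% | 40%* | 70% not exceeded | 70.8% | 62.3% |
| 95% | 80%* | difference exactly 15 | 51.7% | 32.8% |
| 95% | 85%* | 70% clearly exceeded | 30.8% | 13.6% |
| 95% | 55% | planning case | 99.0% | 98.0% |

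**Step 3. What a test of the stated objective would do.** Exact binomial, H0: pT ≤ 0.70, true rate 95%:

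| n in test arm | One-sided level | Cured needed | Actual alpha | Power |
|---|---|---|---|---|
| 35 | 2.5% | 31 | 0.9% | 97.1% |
| 35 | 5% | 30 | 2.7% | 99.3% |
| 30 | 2.5% | 27 | 0.9% | 93.9% |
| 30 | 5% | 26 | 3.0% | 98.4% |

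**Step 4. Single outcomes at 35 per arm (uncorrected chi-square).**

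- 21/35 against 10/35: chi-square p = 0.008, yet the test product cured only 60%.
- 33/35 against 32/35: chi-square p = 0.64, yet 33/35 is well above 70% (exact one-sided p = 0.0005).
- 31/35 against 22/35: difference 9/35 = 25.7 points, p̄ = 53/70, z = 2.51, p = 0.012. The 95% interval for the difference is 6.5 to 44.9 points, so 15 is not excluded.

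**The case against.** The best defence is that section 5.1 also names the comparison with the reference, and that the design and sample size are two-armed, so a two-arm test does answer part of what stands under the primary objective. That is fair as far as it goes, but the comparative sentence carries no hypothesis or margin. The 70% criterion is the one stated in sections 5.1, 5.3 and 10.4.1, and it remains untested.

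Second, objective 5.2 b asks only for superiority, and a chi-square is a valid test of that. The error rates for a claim of more than 15 points apply only if the result is reported that way. This is true of objective b. But section 10.4.1 itself writes 15% into the alternative, so the reading comes from the plan.

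Third, several reference rates above are assumed, and at the planning rates of 95% and 55% the two tests would rarely disagree: 98–99% for the chi-square and 97–99% for the exact test. This stands and limits how often harm would be seen if the planning rates are right. It does not supply the missing test. A high reference rate also cannot be dismissed, since objective 5.2 a sets out to show that it exceeds 70%.

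Fourth, a margin-based test may cost power. This also stands, and the fix allows for it.

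**Conclusion.** The concern holds and must be fixed before analysis. The primary objective as declared has no prespecified test, and the test given in its place cannot support the margin written into its own alternative.

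At 35 per arm with the uncorrected two-sided 5% chi-square, a product sitting exactly at the 70% limit would appear successful in 25% of trials against the protocol's 55% reference rate, and in 71% against an assumed 40%. A product at 95% would miss significance in about 69% of trials against an assumed 85%. At a true 15-point difference the false-claim rate is 25–52%, or 19–33% with continuity correction. The sizes depend on the assumed reference rates, sidedness and correction. The mismatch itself depends on none of these.

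**What to change.** In section 10.4.1, replace the primary hypotheses with H0: pT ≤ 0.70 against Ha: pT > 0.70. Test them by an exact binomial test in the test arm (equivalently, an exact lower confidence limit above 70%) and state the one-sided level. With 35 subjects this requires 31 cured at 2.5% or 30 cured at 5%.

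Then test objective 5.2 b in fixed sequence, choosing one of two forms:

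- **Margin kept.** H0: pT − pR ≤ 0.15 against > 0.15, by a score-type lower limit (Farrington–Manning or Miettinen–Nurminen) above 15%.
- **Plain superiority.** H0: pT − pR ≤ 0, with 15% removed from both the alternative and the sample-size statement.

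The −7.5% non-inferiority step can stay as the fallback after objective b. Objective 5.2 a also has no test; the same exact binomial test in the reference arm would serve.

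**Cost.** These are wording changes, and the primary test needs no new data or subjects. If the 15-point margin is kept, the level decides whether 35 per arm is enough. At 95% against 55%, enumerating the score test gives 86.6% power at one-sided 5% but 77.8% at one-sided 2.5%, just under the stated 80%. Reaching 80% at 2.5% would take 38 per arm by the unpooled formula, or 41 by the score formula (40.06 rounded up). The level and the margin should therefore be fixed together.

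### Section 10.4.1 lets non-inferiority to the reference follow inside the primary analysis with no condition that the 70% cure-rate limit has been met

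*Combined protocol and SAP*

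**What the plan says.** Section 5.1 sets the requirement: "The test product must achieve a cure rate superior to 70% (at the end of day 10, corrected for re-infestation"). Section 10.4.1, headed as the analysis of the primary objective, restates it: "The aim of the study is to show superiority for the cure rate of the test product versus a predefined limit of 70" per cent.

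The hypothesis that follows in 10.4.1 is labelled H0,prim, but it concerns the difference between the arms, p_T − p_R, with an alternative above 15%. A chi-square "test of independence will be used to test the null hypothesis". No one-sample test against 70% is given. The section continues: "In case superiority could not be proven, non-inferiority will be tested". The margin is 7.5 points: "a 7.5% worse cure rate is regarded as clinically not relevant".

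Section 5.2 lists the same step as secondary objective c, directly after objective b (superiority over the reference): "In case that superiority cannot be shown: to show that the test product is non-inferior to reference product regarding cure rate".

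Section 10.2 gives the planning rates: "superiority (superiority margin of 15%) of the test product (cure rate of 95%) over the reference product (cure rate 55" per cent). Section 8.1 plans 35 subjects per group; sections 10.1 and 10.2 give 30.

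**The concern.** The requirement is absolute (above 70%), but the only decision rule written under the primary heading is relative to a comparator planned 15 points below it. The last superiority named in words before the fallback sentence is superiority over 70%. The last one in symbols is superiority over the reference. On either reading, the non-inferiority conclusion does not depend on the 70% limit, and no testing order or success rule elsewhere links the two.

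What is at stake is the headline of the report. A product that has not been shown to exceed 70% could be reported, from the section that defines the primary analysis, as not relevantly worse than the reference.

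**Working it through.** **The plan's own figure.** Section 10.2: 95% v 55%, superiority margin 15 points, 80% power, 5% level. With unpooled variance and a one-sided 5% level:

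n = (1.645 + 0.842)² × (0.55×0.45 + 0.95×0.05) / (0.95 − 0.55 − 0.15)² = 6.18 × 0.295 / 0.0625 ≈ 29.2, so 30 per group.

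This reproduces the 30, so the size was set for superiority by more than 15 points. The same formula gives 86.0% power at 35 per group, not the 80% in section 8.1. The check below uses 35, the number to be enrolled per arm.

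**Assumptions where the plan is silent.**
- 70% limit: exact binomial test, one-sided 5%. P(X ≥ 29 | 35, 0.70) = 0.065 and P(X ≥ 30) = 0.027, so 30/35 (85.7%) is needed.
- Non-inferiority: lower limit of a two-sided 95% Newcombe interval above −7.5 points, in the usual direction. The last sentence of 10.4.1, read literally, reverses the rule.
- Superiority: either a significant uncorrected chi-square in favour of the test product (difference above 0), or a Newcombe lower limit above 15 points.

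**Example: 19/35 (54.3%) cured on reference.** The Newcombe lower limit is (a − b) − √[(a − l_a)² + (u_b − b)²], where a and b are the observed test and reference rates, l_a is the lower Wilson limit for a and u_b is the upper Wilson limit for b.
- 25/35 on test: 0.1714 − √[(0.7143 − 0.5495)² + (0.6953 − 0.5429)²] = 0.1714 − 0.2245 = −5.3 points. Non-inferiority is met; χ² = 2.20, not significant.
- 24/35: lower limit −8.2 points; non-inferiority is not met.
- 26/35: χ² = 3.05, not significant. 27/35: χ² = 4.06, significant (critical value 3.84).
- 31/35: lower limit 13.2 points. 32/35: 16.6 points.

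So non-inferiority without superiority occurs at 25 to 26 test cures if superiority means above 0, and at 25 to 31 if it means above 15 points. The first range lies wholly below 30; the second includes 30 and 31, which pass the 70% test.

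**Chance of each result with fewer than 30 test cures.** Exact sum over all 36 × 36 pairs of two independent binomials with n = 35:

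| True test v reference | Non-inferiority only (superiority = above 0) | Non-inferiority only (superiority = above 15 points) | Superiority (above 0) |
|---|---|---|---|
| 60% v 55% | 12.6% | 18.1% | 5.7% |
| 65% v 55% | 18.9% | 30.8% | 12.5% |
| 70% v 55% | 23.6% | 45.3% | 23.0% |
| 65% v 50% | 24.8% | 45.7% | 22.7% |
| 90% v 55% | 3.0% | 11.2% | 9.2% |
| 95% v 55% (planned) | 0.15% | 0.63% | 0.54% |

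The last column shows that the gap is not confined to non-inferiority. At 70% v 55%, superiority over the reference while missing 30/35 is about as likely as the non-inferiority-only result.

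**The case against.** The strongest reply is that the plan already ranks these results. Section 5.1 keeps the 70% requirement as primary, section 5.3 keeps the test product's own cure rate as the primary endpoint, and 5.2c makes non-inferiority secondary, triggered by failure of 5.2b. A careful report would show the primary objective as missed whatever the comparison gave. This stands, and it limits the point. A reader might infer that non-inferiority is designed to rescue a failed primary objective, or that the two conclusions contradict each other. The documents do not support that: the conclusions answer different questions. What remains is that 10.4.1 carries the fallback under the primary heading, labels the two-arm test as primary, and contains no 70% test.

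A reader might also infer that every non-inferiority-only result fails the 70% limit. With superiority meaning a difference above 0, this is so for reference counts of 15 to 22 out of 35. It fails under the 15-point margin to which the trial was sized, as the 19/35 example shows.

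A third tempting reading is that a product curing about 48% could readily be claimed non-inferior. The boundary is indeed 55 − 7.5 = 47.5%, but at a true 48% v 55% the chance of showing non-inferiority is 2.8%.

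Two further replies are fair. The 30/35 threshold is an assumption, since the plan names no test against 70%; at 19/35 reference cures, non-inferiority already needs 25/35 = 71.4% observed. And 55% is only a planning rate, while objective 5.2a hopes to show that the reference itself exceeds 70%. Neither supplies the missing condition.

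**Conclusion.** The point holds as a gap in the decision rule. Section 10.4.1, read alone, lets the primary analysis end in a non-inferiority conclusion without the 70% limit being met, and no other section prevents this.

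Its practical size depends on the truth. It is about 13% to 25% at true test rates of 60% to 70% against 50% to 55% when superiority means above 0, and up to about 45% at 70% v 55% when it means the 15-point margin. It is about 0.2% to 0.6% if the planned 95% v 55% is right. These figures rest on 35 per arm, the Newcombe two-sided 95% limit and the exact one-sided 5% test; the structural gap does not depend on them. It deserves correction because it matters most when the product performs below expectation.

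**What to change.** - In 10.4.1, make the fallback sentence refer to superiority to the reference product, and move it, with the two-arm hypotheses, under secondary objectives b and c.
- State that the primary objective is met only if the test product's Day 10 cure rate is shown to exceed 70%, and name the one-sample test that decides this.
- State that both comparative results, superiority and non-inferiority, support a confirmatory claim only after that. Otherwise report the difference with its 95% interval alongside the missed primary objective. Conditioning non-inferiority alone would be lopsided, as the last column of the table shows.

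This takes a few sentences in 5.2 and 10.4.1 and no extra subjects or data. The cost is that the sponsor loses confirmatory comparative claims when the 70% requirement is missed. If superiority means above 0, a non-inferiority-only claim will then rarely be available.
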